5.1.2.6 Hydrocephalus

Hydrocephalus is included as a warning in the labelling of one marketed IT-administered 2'-MOE chimeric ASO. No hydrocephalus was observed in the completed RO7234292 Phase I/IIa MAD study (ISIS 443139-CS2). *A single case of hydrocephalus following chemical meningitis has been observed in the Q4W cohort of the ongoing Phase II OLE Study BN40697 to date. For details please see the RO7234292 Investigator's Brochure; for management guidelines, see Section 5.1.3.3.*

5.1.2.8 Potential Risk due to Reduction of Target Protein HTT

By specifically targeting mRNA from both HTT alleles, RO7234292 can lower levels of both mHTT and normal "wild-type" huntingtin (wtHTT) protein in all patients, regardless of other genetic variations. The ASO modality provides partial, transient, reversible, and titratable HTT lowering. Partial HTT lowering is safe and well tolerated in normal rodents and non-human primates, as shown in multiple studies using ASOs and non-reversible approaches. Furthermore, no safety signals of concern emerged in non-clinical studies or in the completed Phase I/IIa study of RO7234292 in adults with HD (see RO7234292 Investigator's Brochure), in which partial lowering was achieved.

Transgenic mice expressing human mHTT develop progressive HD-like phenotypes that recapitulate many aspects of HD in humans. ASO-mediated mHTT lowering provides therapeutic benefits and often restores normal functioning in transgenic and fully humanized animal models of HD, with generally similar results regardless of whether wtHTT is also lowered. Moreover, no detrimental effects of partial wtHTT lowering in animal models have been reported in multiple studies using ASOs and non-reversible approaches.

Still, the current understanding of the diverse cellular functions of HTT suggests potential theoretical risks associated with reducing total HTT levels in people with HD. More than 2 decades of research findings implicate HTT in a wide array of cellular functions, including microtubule-based transport, F-actin-based trafficking, Rab-based trafficking, brain-derived neurotrophic factor transport, ciliogenesis, transcription, chromatin modification, post-transcriptional gene-expression regulation, neurogenesis, synaptogenesis, synaptic plasticity, signaling pathways, cell stress responses, cell survival, selective macro-autophagy, and DNA damage repair, as detailed in a recent review article (Liu and Zeitlin 2017).

Although functional HTT (mutant or wild-type) is essential for embryogenesis, near complete genetic ablation of HTT has little or no reported neurological effect in normal adult animals. However, complete ablation of wtHTT protein expression throughout life results in a worsening motor phenotype and, in male transgenic mice, age-dependent emergence of brain atrophy and decreased testicular size (Van Raamsdonk et al. 2005). In contrast, decreases in mHTT expression ameliorate disease and increases in mHTT exacerbate disease in animal models of HD, regardless of concomitant changes in wtHTT levels.

No clinically significant new neurologic events were observed in the completed Phase I/IIa study.

As a precaution a full neurological examination will be conducted as indicated in [Appendix 1](#).

5.1.3 Management of Patients Who Experience Adverse Events

5.1.3.1 Dose Modifications

No dose adjustment from the planned treatment is permitted in this study, whether by varying the amount of study drug volume injected or the frequency of procedure per protocol (i.e., all participants will receive 20 mL of study drug per injection at the prespecified dose level).

5.1.3.2 Treatment Interruption

RO7234292 treatment may be temporarily suspended in patients who experience toxicity considered to be related to study drug. If RO7234292 has been withheld for >3 days because of toxicity, the patient should be discontinued from RO7234292, unless

resumption of treatment is approved following Investigator discussion with the Medical Monitor. RO7234292 treatment may be suspended for reasons other than toxicity (e.g., surgical procedures) with Medical Monitor approval. The Investigator and the Medical Monitor will determine the acceptable length of treatment interruption.

5.1.3.3 Management Guidelines

Guidelines for management of specific adverse events are outlined in [Table 1](#). Additional guidelines are provided in the subsections below.

Initial clinical laboratory tests with results meeting criteria for withholding study drug must be repeated on new specimens as soon as possible, and results must be available prior to administering the next dose of study drug. In general, patients who do not reach the stopping rule may continue dosing; however, the Investigator and Sponsor should confer as to whether additional close monitoring of the patient is indicated.

Table 1 Guidelines for Management of Patients Who Experience Adverse Events

Event	Action to Be Taken
Elevations in CSF WBC count or proteins or suspected meningitis, radiculitis, arachnoiditis, hydrocephalus , or other acute neurologic symptoms	
 Withhold study drug if diagnosis of meningitis, radiculitis, arachnoiditis, hydrocephalus or acute neurologic symptoms is suspected and initiate appropriate diagnostic work-up as indicated. Clinical signs and symptoms of hydrocephalus (e.g. new onset of persistent or worsening gait disturbance, change in level consciousness/ cognition, changes in continence, or a combination of all three signs) are required for diagnosis of suspected hydrocephalus. Clinical signs and symptoms of meningitis (e.g., headache, stiff neck, and fever) plus confirmatory WBC count are required for diagnosis of suspected meningitis and clinical signs and symptoms are required for diagnosis of radiculitis, arachnoiditis or acute neurologic symptoms. Isolated low-level (e.g., 5 to 50/μL WBC count) elevations in CSF WBC count without clinical symptoms do not meet criteria for diagnosis of suspected meningitis. In the event of persistent back pain or fever, promptly consider imaging investigation to exclude spinal abscess and discuss with Medical Monitor. The Medical Monitor should be consulted in all cases of WBC count CSF elevations, or a change from baseline in CSF proteins greater than twice baseline, or where there is uncertainty to discuss next steps of patient management in the study. If a diagnosis of suspected meningitis, radiculitis, arachnoiditis, hydrocephalus or acute neurologic symptoms is refuted, the study drug may be resumed after consultation with the Medical Monitor. In the event meningitis, radiculitis, arachnoiditis, hydrocephalus or acute neurologic symptom diagnosis is confirmed, standard-of-care therapies should be instituted as indicated.

ALT=alanine aminotransferase; AST=aspartate aminotransferase; CrCl=creatinine clearance; CSF=cerebrospinal fluid; eGFR=estimated glomerular filtration rate; INR=international normalized ratio; ULN=upper limit of normal; WBC=white blood cell.

Table 1 Guidelines for Management of Patients Who Experience Adverse Events (cont.)

Event	Action to Be Taken
Thrombocytopenia	
 • If platelet count is $\leq 100,000/\text{mm}^3$: 
 Monitor platelet count weekly. • If platelet count is $\leq 75,000/\text{mm}^3$ and $> 50,000/\text{mm}^3$ in the absence of major bleeding or clinically relevant non-major bleeding: 
 Withhold study drug until the platelet count has recovered to $> 100,000/\text{mm}^3$. The suitability of the patient for continued dosing and frequency of monitoring should be discussed with the Medical Monitor. • If platelet count is $\leq 50,000/\text{mm}^3$: 
 Permanently discontinue. Monitor platelet counts daily until two successive values show improvement. Then monitor every 2 to 3 days until platelet count is stable, and at least weekly until platelet count returns to normal. Administration of steroids may be considered for patients whose platelet count is $< 25,000/\text{mm}^3$.
Decreased renal function	
 • Withhold study drug in the event of a persistent (> 2 weeks) decrease of eGFR or CrCl or increase in creatinine, as defined below: 
 1. eGFR or CrCl $< 60 \text{ mL/min}/1.73 \text{ m}^2$. 2. Creatinine level increase of $2.0 \times$ above baseline. • Study Drug may be resumed when follow-up test results show that the patient no longer meets the dose interruption criteria.

ALT=alanine aminotransferase; AST=aspartate aminotransferase; CrCl=creatinine clearance; CSF=cerebrospinal fluid; eGFR=estimated glomerular filtration rate; INR=international normalized ratio; ULN=upper limit of normal; WBC=white blood cell.

Table 1 Guidelines for Management of Patients Who Experience Adverse Events (cont.)

Elevated liver enzymes	
 ALT or AST is $> 3 \times$ ULN: 
 Monitor weekly until ALT and AST return to $\leq 1.2 \times$ ULN. Further investigation into the liver enzyme elevations may include hepatitis serologies and other diagnostic tests at the discretion of the Investigator in consultation with the Medical Monitor. Withhold study drug in the event of liver enzymes that meet the following criteria without an alternative explanation (as discussed with the Medical Monitor): 
 ALT or AST $> 5 \times$ ULN. ALT or AST $> 3 \times$ ULN, combined with total bilirubin $> 2 \times$ ULN or INR > 1.5. ALT or AST $> 3 \times$ ULN coinciding with new appearance of fatigue, nausea, vomiting, right upper quadrant pain or tenderness, fever, rash, and or concomitant eosinophilia. Discontinue study drug permanently if levels do not return to baseline after 30 days.
------------------------	--

ALT=alanine aminotransferase; AST=aspartate aminotransferase; CrCl=creatinine clearance; CSF=cerebrospinal fluid; eGFR=estimated glomerular filtration rate; INR=international normalized ratio; ULN=upper limit of normal; WBC=white blood cell.

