5.1.1 Known Risks Associated with Lumbar Puncture

In the completed Phase I/IIa study, 46 patients were randomized to receive RO7234292 (n=34) or placebo (n=12). The most commonly reported adverse events across all treatment groups included procedural pain (54%) and post-lumbar puncture syndrome (37%). One patient who received placebo reported a serious adverse event of post-dural-puncture headache.

In the ongoing Phase II OLE Study BN40967 (15-month data cut), potential post-lumbar puncture adverse events (including procedural pain, post-lumbar puncture syndrome, post-procedural discomfort, *puncture site pain, headache, migraine, nausea, dyspepsia, backpain, malaise, and paraesthesia*) occurring within 72 hours of drug administration were summarized per cohort. For the Q4W cohort (n= 23), 35 events were reported in 14 (60.9%) patients; for the Q8W cohort (n=23), 36 events were reported in 12 (65.2%) patients.

Many of the complications associated with lumbar puncture can be avoided by the mandatory use of a 24G atraumatic needle with a stylet, adherence to procedural guidelines (see lumbar puncture manual and instructional video), and careful assessment of the patient, including neurologic examination with fundoscopy both prior and post the lumbar puncture procedure. Lumbar puncture should be avoided when contraindication is present.

CSF leakage is more likely with larger bore needles. To minimize this risk, a 24G atraumatic needle will be used. Training for use of the 24G atraumatic needle will be provided prior to initiation of lumbar puncture in the study, as will a review of extension tubing use and the need to gently aspirate CSF for timely collection. If headache with characteristics of low-pressure syndrome is present after the procedure and persists despite standard-of-care treatment, a blood patch should be considered. Formation of a subarachnoid epidermal cyst (i.e., when a skin plug is introduced into the arachnoid space) can be avoided by use of a needle with stylet, which is mandatory. Rarely, brain herniation can occur in the setting of lumbar puncture and increased intracranial pressure.

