5.1.1.4 Known Risks Associated with an Indwelling Catheter

Insertion of an intrathecal catheter carries the same risks as a lumbar puncture, with additional risks of catheter blockage, disconnection or retraction.

Of note, in the current study, 2 out of 6 patients developed a lumbar abscess after having had the catheter implanted for 4 days.

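### In Table 1, suspected meningitis already requires a confirmatory white-cell count, and possible spinal abscess showing only as back pain or fever has no specific hold or resume rule before dose 2

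*Protocol*

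**What the plan says.** All of this is in the central nervous system row of Protocol Table 1 (5.1.3.3) unless marked otherwise.

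- **Hold.** "Withhold study drug if diagnosis of meningitis, radiculitis, arachnoiditis", hydrocephalus or acute neurologic symptoms is suspected, and start the work-up.
- **Meningitis.** Signs such as headache, stiff neck and fever "plus confirmatory WBC count are required for diagnosis of suspected meningitis".
- **Other limbs.** By contrast, "clinical signs and symptoms are required for diagnosis of radiculitis, arachnoiditis or acute neurologic symptoms". Hydrocephalus is also defined by signs alone.
- **Abscess.** For persistent back pain or fever: "promptly consider imaging investigation to exclude spinal abscess and discuss with Medical Monitor".
- **Resumption.** If one of the named diagnoses is refuted, "the study drug may be resumed after consultation with the Medical Monitor". Abscess is not among them.
- **Default, in the text above the table.** "In general, patients who do not reach the stopping rule may continue dosing"; the sentence goes on to ask the Investigator and Sponsor to confer about closer monitoring.
- **History (5.1.1.4).** In this study, "2 out of 6 patients developed a lumbar abscess after having had the catheter implanted for 4 days".
- **Dose 2 (4.3.2).** A 20 mL injection through a new lumbar puncture on Day 29.

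**The concern.** A hold on suspicion should act before the diagnosis is settled. Here the meningitis limb cannot act until a confirming count exists. For spinal abscess, the serious catheter complication already seen in this study, the row's wording is weaker than for radiculitis or arachnoiditis in the same cell: imaging is to be considered and the case discussed, with no instruction to hold drug.

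This matters once per patient. Dose 1 goes in through the catheter, so Day 29 is the only later dose on which the row can act. What is at stake is a fresh puncture and a 20 mL injection in a patient who may have an unrecognised infection in or near the spinal canal.

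**Working it through.** The plan gives no figure to reproduce. The check is mainly a comparison of texts, with some arithmetic for size.

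**1. The row, limb by limb.**

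| Condition | Signs alone enough for suspicion? | In withhold bullet | In resume bullet |
|---|---|---|---|
| Meningitis | No, a WBC count as well | Yes | Yes |
| Radiculitis, arachnoiditis | Yes | Yes | Yes |
| Hydrocephalus | Yes | Yes | Yes |
| Acute neurologic symptoms | Yes (term not defined) | Yes | Yes |
| Spinal abscess | Not stated | No | No |

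The meningitis clause does not say which WBC count is meant. I read it as CSF, from the row heading and the sentence that follows it. Section 5.1.1.3 sends the management of suspected meningitis to this table, so no other text supplies a definition.

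**2. When a count would be available (Appendix 1).** CSF safety samples are scheduled on Days 1, 2 and 3, then Day 29: 29 − 3 = 26 days without a scheduled count. The Day 29 sample comes from the dosing-day puncture. CRP/ESR is drawn up to Day 4, then on Day 29: 29 − 4 = 25 days. No visit is scheduled between discharge on Day 4 and Day 28. A patient who falls ill in between has no count unless an unscheduled puncture is done.

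**3. Comparisons within the protocol.** Hydrocephalus appears in both dosing bullets on the strength of one case in the open-label extension (5.1.2.6). Lumbar abscess, with two cases in this study, appears in neither. For suspected spinal hematoma, 5.1.1.2 says that prompt MRI should be done; for abscess, imaging is only to be considered. The puncture contraindications in 5.1.1 do not list local spinal infection.

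**4. Abscess count.** 2/6 = 33.3%. Exact (Clopper-Pearson) 95% limits: lower = Beta quantile at 0.025 with parameters (2, 5) = 4.3%; upper = Beta quantile at 0.975 with parameters (3, 4) = 77.7%. This describes the superseded 4-day catheter only.

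**5. How often a back-pain rule might act.** The extension-study summary in 5.1.1 counts potential post-puncture events within 72 hours, a list that includes "puncture site pain, headache, migraine, nausea, dyspepsia, backpain, malaise, and paraesthesia". In the every-4-weeks cohort, 14/23 = 60.9% of patients had one. The every-8-weeks cohort is printed as 12 patients (65.2%), but 12/23 = 52.2% and 15/23 = 65.2%, so that figure lies between 52% and 65%. The rate of back pain alone is not given. Early back pain is thus no basis for an automatic hold, and the word persistent in the present trigger should stay.

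**6. Price of a lost dose.** One missed second dose is 1/4 = 25% of a planned dose group. The Day 29 window is ±2 days, and 4.6.1 allows no replacement.

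**The case against.** The strongest reply is that no patient is left unprotected. The same row holds drug for suspected acute neurologic symptoms on signs alone, and new headache with stiff neck and fever fits that limb naturally, as would an abscess with radicular signs. Once signs and a count are both present, the meningitis limb itself applies. Section 4.5 is mandatory: a dose is given only if the clinical assessment and local laboratory values are acceptable. Section 4.6.1 requires permanent discontinuation for any condition judged to jeopardise safety, and 5.1.3.2 permits suspension. A physical examination, temperature and local hematology are scheduled on Day 28, and a neurologic examination precedes each dose. CRP/ESR is a local test already drawn on Day 29, and Appendix 6 puts drug administration last. Any uncertainty goes to the Medical Monitor. The lumbar puncture manual, which is not among the documents, may bar puncture in local infection.

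Most of this stands. A reader might infer that the protocol lets a patient with suspected spinal infection be dosed, or that a hold for meningitis rests on general checks alone. Neither follows. The general default is permissive and does not override 4.5 or 4.6.1, and the row has its own limb that can catch meningitis early.

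What remains is narrower. Acute neurologic symptoms and acceptable values are both undefined, so the hold turns on how an individual investigator reads them. The toxicity clause of 5.1.3.2 covers drug-related toxicity, which a catheter abscess would not ordinarily be. Persistent back pain or fever without neurologic signs meets no specific hold.

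**Conclusion.** The point holds in a limited form. The meningitis hold is circular as worded; before a count exists, it depends on an undefined neighbouring limb or on judgement under 4.5 and 4.6.1. Possible spinal abscess showing only as persistent back pain or fever has no specific hold and no resume rule. Those gaps rest on the text itself, apart from the reading of the count as a CSF count.

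The clinical size cannot be estimated. It would be wrong to carry 33% forward: the catheter now stays 48 hours, MRSA screening, skin preparation, cultures and CRP/ESR have been added, and the documents do not say when the two abscesses appeared relative to Day 29. This is a cheap patient-safety improvement. It is not evidence that the plan directs unsafe dosing.

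**What to change.** 1. **Meningitis.** Withhold on the clinical picture (headache, stiff neck and fever together) and use the CSF white-cell count to confirm or refute it.
2. **Abscess.** Keep the present trigger of persistent back pain or fever for imaging and Medical Monitor discussion. Add suspected spinal or lumbar abscess to the withhold and resume bullets, with no lumbar puncture or dosing until it is excluded. I would not add a time cut-off for back pain: the documents give no basis for one, and it could be narrower than the current wording.
3. **CRP/ESR.** Move the Day 29 local draw to the Day 28 blood draw, with the coagulation and platelet sample that 4.5.5 already requires to be reviewed before the puncture. Review the result with the catheter-tip culture and the Day 1 to 3 CSF cultures before dose 2. The check in 4.5 stays as written.

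The cost is new wording in one table row and one sample moved by a day. The downside is an occasional delayed or missed second dose, each one 25% of a group of four and not replaced, and imaging in some patients who might otherwise only have been discussed.

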4.5 STUDY ASSESSMENTS

The schedules of activities to be performed during the study are provided in [Appendix 1](#) and [Appendix 2](#). All activities should be performed and documented for each patient.

Patients will be closely monitored for safety and tolerability throughout the study. Patients should be assessed for toxicity prior to each dose; dosing will occur only if the clinical assessment and local laboratory test values are acceptable.

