4.5.5 Collection of Cerebrospinal Fluid (Lumbar Puncture Procedure)

*Skin (groin area) and nose swabs will be taken during screening to test for Methicillin-resistant *Staphylococcus aureus* (MRSA). If the MRSA screening result is positive, treatment for decolonization (as per local standard procedure) should be administered for 5 days prior to catheter insertion.*

In preparation for the catheter insertion, patients will be required to remove all body piercings, make up, and nail polish and to cleanse the entire body (including hair) with antibacterial soap on Day -2 or Day -1.

Within 72 hours prior to performing each scheduled lumbar puncture or IT catheter insertion, local laboratory analysis of coagulation factors (international normalized ratio [INR], activated partial thromboplastin time [aPTT], prothrombin time [PT]) and platelets must be conducted and the results reviewed. Each lumbar puncture should be performed at approximately the same time at each visit (ideally in the morning between 8:00 a.m. and 12:00 noon or in the early afternoon between 12:00 noon and 3:00 p.m.) to minimize potential diurnal variation of CSF parameters. *A 20 mL sample will be taken at predose after the IT catheter has been inserted. Subsequently, during the CSF sampling period until 48 hours postdose, a maximum 5 mL of CSF fluid will be collected (via the IT catheter) at each timepoint indicated in [Appendix 2](#). In addition, up to 2 mL CSF sample will be collected for daily CSF safety testing, including culture, during the indwelling-catheter period at the timepoints indicated in [Appendix 1](#) and [Appendix 2](#). Upon removal, the catheter tip should be sent for culture.*

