4.6.1 Study Treatment Discontinuation

Patients must permanently discontinue study treatment if they experience any of the following:

- Any medical condition that the Investigator or Sponsor determines may jeopardize the patient's safety if he or she continues to receive study treatment
- Investigator or Sponsor determination that treatment discontinuation is in the best interest of the patient
- Pregnancy
- Any event that meets stopping criteria defined in Section [5.1.3](#)

The primary reason for study treatment discontinuation should be documented on the appropriate eCRF. Patients who discontinue study treatment prematurely will not be replaced.

All patients who withdraw or discontinue from study treatment early will be asked to return to the clinic for the early termination visit within $28 \text{ days} \pm 14 \text{ days}$ after the last dose of study drug.

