5.1.1.2 Spinal Hematoma

Post-lumbar puncture spinal hematoma is a very rare but important potential risk that can present as persistent back pain, radicular pain, new sensory or motor symptoms, sphincter disturbance, or meningism. Prompt magnetic resonance imaging scanning should be performed if suspicion of spinal hematoma arises. Patients with susceptibility to bleeding, patients with coagulopathy, and patients receiving anticoagulant therapy are at an increased risk of spinal hematoma and will be excluded from this study (see Section 4.1.2). Management of spinal hematomas should be in consultation with neurosurgical colleagues.

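### Table 1 withholds drug at platelets above 50,000 and up to 75,000/mm³ only if the patient is not bleeding, so a bleeding patient with the same count gets a weaker written rule

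*Protocol*

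**What the plan says.** The thrombocytopenia row of Table 1 (Protocol 5.1.3.3) has three tiers:

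- At or below 100,000/mm³: count platelets weekly.
- At or below 75,000 and above 50,000/mm³, "in the absence of major bleeding or clinically relevant non-major bleeding": hold the drug until the count is back above 100,000/mm³, and discuss further dosing and monitoring frequency with the Medical Monitor.
- At or below 50,000/mm³: stop permanently, with daily counts at first.

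Two sentences ahead of the table govern how it is applied. The first concerns results that call for withholding: "Initial clinical laboratory tests with results meeting criteria for withholding study drug must be repeated on new specimens as soon as possible", with the repeat result in hand before the next dose. The second sets the default: "In general, patients who do not reach the stopping rule may continue dosing; however, the Investigator and Sponsor should confer" on whether closer monitoring is needed.

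Section 5.1.2.3 refers platelet management to Table 1. Section 4.6.1 refers stopping criteria to Section 5.1.3, which contains Table 1. The SAP has no rule on this point.

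**The concern.** Bleeding at a low platelet count should lead to an action at least as strong as the same count without bleeding. As worded, the qualifier does the opposite: bleeding takes the patient out of the withholding tier and no other tier picks the patient up. This is most likely a drafting omission, with a companion line for bleeding patients intended but never written.

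The liver row of the same table works the expected way. ALT or AST above 3 times the upper limit of normal calls for weekly monitoring alone, and the same elevation with new clinical symptoms calls for withholding. There, clinical signs raise the action. In the platelet row they remove it, and no reason is given.

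The consequence concerns the next injection. Section 4.3.2 has the second dose given by lumbar puncture, and Section 5.1.1.2 says: "Patients with susceptibility to bleeding, patients with coagulopathy, and patients receiving anticoagulant therapy are at an increased risk of spinal hematoma". For the higher-risk patient, whether the Day 29 procedure goes ahead is left to general judgment. For the lower-risk patient with the same count, the table decides.

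**Working it through.** No sample size, power or error rate is involved. The check is a literal application of the rule.

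**Step 1. Cross the platelet tiers with bleeding status** (Table 1, thrombocytopenia row).

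| Platelets (/mm³) | No major or clinically relevant non-major bleeding | Such bleeding present |
|---|---|---|
| >75,000 to ≤100,000 | Weekly count | Weekly count |
| >50,000 to ≤75,000 | Weekly count, withhold to >100,000, Medical Monitor discussion | Weekly count only |
| ≤50,000 | Permanent discontinuation, daily counts | Permanent discontinuation, daily counts |

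The middle row is the only one in which bleeding changes the action, and it weakens it.

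**Step 2. Count the actions at 60,000/mm³.**

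- Without bleeding: weekly count, withhold, recovery level of >100,000, Medical Monitor discussion (4 from Table 1), plus the repeat specimen before the next dose (1 from the text of 5.1.3.3). 4 + 1 = 5.
- With bleeding: the ≤100,000 condition is met (weekly count), the middle condition fails on its qualifier, and ≤50,000 is not met. No withholding criterion is met, so the repeat-specimen rule is not triggered. 1 of the 5 applies.

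**Step 3. Look for another rule that fills the cell.**

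- *Other Table 1 rows.* The first row withholds for suspected meningitis, radiculitis, arachnoiditis, hydrocephalus or acute neurologic symptoms. It would catch a bleed that causes neurologic symptoms, but it does not depend on platelets or bleeding as such.
- *Section 4.5, pre-dose check:* "dosing will occur only if the clinical assessment and local laboratory test values are acceptable". Mandatory, but it does not say which values are acceptable.
- *Section 4.5.5, within 72 hours before each lumbar puncture:* local coagulation tests "and platelets must be conducted and the results reviewed". It does not say which result bars the procedure.
- *Section 4.6.1, permanent discontinuation:* "Any medical condition that the Investigator or Sponsor determines may jeopardize" the patient's safety. This rests on judgment. Its stopping-criteria clause leads back to Section 5.1.3.
- *Section 5.1.3.2, interruption:* "RO7234292 treatment may be temporarily suspended in patients who experience toxicity considered to be related to study drug". Permissive, and tied to relatedness.
- *Section 5.1.1, contraindications to lumbar puncture.* Those named are cardiorespiratory instability, herniation, raised intracranial pressure and focal neurologic findings. Neither platelets nor bleeding is named, though the list is not presented as complete.
- *Section 5.1.3.3* announces further guidelines in subsections after the table, but Section 5.2 follows directly.

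None of these supplies a threshold, a recovery level or a required Medical Monitor discussion for this patient.

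**Step 4. Size the exposure.** Section 4.1.2 excludes counts below normal, allowing 125,000 to 150,000, so the band can in practice be reached only after dose 1. That leaves one dose per patient, on Day 29: 1 × 12 = 12 doses at the planned size and 1 × 20 = 20 at the maximum. Section 5.1.1.4 shows that at least 6 patients had already been catheterized when Version 4 was written. If all 6 had also passed Day 29 (an assumption), a correction could still affect 12 − 6 = 6 to 20 − 6 = 14 doses.

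**The case against.** The strongest reply accepts the gap and disputes its weight. Table 1 is guidance, and the default on continued dosing is hedged. A clinician told to withhold at 60,000/mm³ without bleeding would hardly inject intrathecally at the same count with bleeding. The pre-dose check is mandatory, and Section 4.6.1 obliges discontinuation once safety is judged to be in jeopardy. Section 5.1.1 says to avoid lumbar puncture when contraindicated. Serious bleeding reaches the sponsor within 24 hours (Sections 5.2.2 and 5.4). A dose held more than 3 days for toxicity brings in the Medical Monitor under Section 5.1.3.2. A lumbar puncture manual that we have not seen may set a platelet limit.

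Much of this stands as a description of what would probably happen. It does not supply the missing rule: each provision rests on judgment or concerns reporting, and the Medical Monitor step follows only once someone has decided to hold the dose. The sponsor wrote a numeric rule for the non-bleeding patient with the same provisions in place, so they do not explain why the bleeding patient has none.

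Two narrower points have some force. First, the count depends on how actions are grouped. Table 1 alone gives 4 against 1. If the investigator–sponsor conferral is credited to the bleeding patient, Section 5.1.3.3 gives 5 against 2. The direction is the same, and that conferral concerns monitoring, not withholding. Second, losing the repeat-specimen rule matters mainly when the low count first appears in the sample taken just before the puncture, because weekly counts and the 72-hour check otherwise produce new specimens anyway.

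**Conclusion.** The concern holds. Read literally, the withholding rule for counts above 50,000 and up to 75,000/mm³ is weaker for a patient who is bleeding than for one who is not: one of five explicit actions applies instead of all five. The fault lies in a written safety rule and touches no endpoint or analysis.

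The practical exposure is low. It needs a count in a 25,000-wide band, concurrent significant bleeding and failure of the general safeguards, before a single remaining dose. Section 5.1.2.3 reports no clinically significant platelet reduction with this drug so far, but keeps thrombocytopenia as a potential risk because of related antisense drugs given systemically.

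The conclusion rests on the protocol text. If the lumbar puncture manual sets a platelet or bleeding limit, the procedure itself may be protected, but Table 1 would still be wrong as written. The correction is worth making because it costs almost nothing and the table exists for rare events of this kind.

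**What to change.** Delete the bleeding qualifier from the second tier of the thrombocytopenia row. Withholding, recovery above 100,000/mm³ and the Medical Monitor discussion then apply with or without bleeding, and the repeat-specimen rule follows. This is a minimum: a bleeding patient could resume on the same numeric terms, but only after the Medical Monitor discussion of suitability.

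If the sponsor intended something stricter, add a line instead: *>50,000 to ≤75,000/mm³ with major or clinically relevant non-major bleeding: permanently discontinue*. That line should also state the monitoring (for example, as for ≤50,000/mm³) and define the two bleeding terms, which the protocol does not do.

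Section 4.6.1 needs no change, since it already points to Section 5.1.3. The cost is one deleted phrase or one added line with its definitions. No procedure, visit or sample is added.
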